1.6.2 Multiple testing

P-values will not be corrected for multiple testing. The secondary outcomes are testing the robustness of the findings, by examining if the pattern is similar 1) when milder illness is included, 2) with narrower COVID-19 symptom classifications, and 3) for the separate components of the composite outcome. Consequently, $p \leq 0.05$ will not be employed as a threshold for statistical significance for secondary outcomes.

1.6.3 Missing data

No outcome data will be imputed. However, for a particular event, we will assume that it was not caused by an infection if no information is obtained. Some dates of events may be imprecise (e.g., unknown date of consultation or only month of event known) – such dates will be allocated to the midpoint of the range of possible dates. As all individuals are followed for mortality through the HDSS, individuals whom we were not able to contact by telephone will still contribute to the assessment of the main outcome.

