#### **Outcomes:**

**Primary outcome:** Composite outcome of the first of death, hospitalisation for infection and/or consultation for infection at the health centre

**Secondary outcomes:** Episodes with self-reported infectious disease morbidity. Episodes with self-reported infectious disease morbidity suspected to be caused by COVID (three or more of the following: fever, cough, sore throat, extreme fatigue, loss of smell/taste). Either of the components of the composite outcome described above included repeated events.

**Statistical analysis:** Data will be analysed in Cox proportional hazards models, with time since randomization as the underlying time, to provide hazard ratios (HRs) with 95% CIs for comparison of the intervention and control groups. With the exception of the primary outcome, data will be analysed as a multiple failure time data set. Age in groups of 5 years and suburb will be adjusted for. Clustering within houses will be adjusted for.

**Sample size:** The Bandim Health Project has purchased 1700 doses of OPV. The trial will include participants until the 1700 doses have been used. With a samples size of 3400, half getting OPV, the trial can show a reduction in the combined risk of mortality (which has been around 2% in this age group in our study area) and severe morbidity after 6 months of follow-up from a total of 10% to 7.2% (i.e. a 28%

reduction) with 80% power and alpha of 0.05. Since only individuals above the age of 50 years are eligible to enter the trial, only few houses will have several participants and we expect a very limited effect of clustering.

**Explanation to participants:** Participants will be given thorough information about Coronavirus, about precautions to be taken, and about the study (Appendix 2).

**Timeline:** A Gantt diagram is presented in Figure 1.

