1.5.2. Secondary outcomes

The secondary outcomes are other measures of infectious disease morbidity (prespecified: a and b, specified after trial initiation: f) and the three separate components of the composite outcome (c, d, and e).

a) Episodes with self-reported infectious disease morbidity: Through the telephone follow-up any reported episode which includes Common cold, Cough, Fever, Breath-lessness, Vomiting, Diarrhoea, Sore throat, or Body aches will be counted as an infectious disease episode. Following an infection, the person will re-enter the at-risk-population 2 weeks later.

b) Episodes with self-reported infectious disease morbidity suspected to be caused by COVID-19: Through the telephone follow-up any reported episode which includes three or more of the following: fever, cough, sore thought, extreme fatigue, or loss of smell/loss of taste). Following an infection, the person will re-enter the at-risk-population 2 weeks later.

c) Mortality: All-cause mortality: Death due to any cause during the follow-up period. If there are cases of inconsistency between different sources of information, the HDSS information will be considered superior.

d) Hospital admission: Hospital admission for infectious disease. Self-reported admission with symptoms or diagnosis classified as caused by infection. Analysed as a repeated event. Following an admission, the person will re-enter the at-risk-population 2 weeks later.

e) Consultations for infectious disease: Consultation for infectious disease registered at one of the two health centres. Analysed as a repeated event. Following a consultation, the person will re-enter the at-risk-population 2 weeks later.

f) Reported consultations: Any consultation for infectious disease reported to have occurred at any health facility.

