1.6 Statistical analyses

1.6.1 Statistical model

The outcome rates will be compared by randomisation arm in Cox proportional hazards models, with time since randomization as the underlying time, to provide hazard ratios (HRs) with 95% CIs. The main results will be adjusted for age (in 5-year age-bands) and zone (based on which the randomisation was stratified). Clustering within houses will be adjusted for. With the exception of the primary outcome, data will be analysed as a multiple failure time data set. All statistical tests will be 2-tailed and $p \leq 0.05$ considered statistically significant.

Prior to implementing the trial, stories of experimental COVID-19 vaccines planned to be tested in Africa had been circulating on social media, and many perceived the OPV, which we were providing in the present trial, as one of these experimental vaccines. We have therefore encountered high refusal rates, especially in the intervention arm. As this may have resulted in baseline imbalances, we will present both the 'crude' result (only adjusted for age and zone) and adjusted results where we will adjust for background factors which affect the estimated effect of OPV on the primary outcome by more than 10%. The background factors to be investigated are presented in Box 1.

In subsequent analyses of the trial dataset, we intend to use targeted maximum likelihood estimation (TMLE) (section 2.6.2). These analyses will be reported later.

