2.6. Further sensitivity analyses

2.6.1 Narrower outcome definitions

In sensitivity analyses we will explore if the conclusions are robust to:

Narrower definitions of the planned outcomes:

- Suspected infectious deaths rather than all cause deaths
- Severe infections with reported loss of weight
- Infections with reported COVID-19 diagnoses, tests performed and positive tests

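### Admissions and consultations of unknown cause are coded as not infection, and no planned analysis varies that coding or counts these events by arm

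*SAP*

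**What the plan says.** The primary outcome (SAP 1.5.1; SAP 2.2, Table 1) is the earliest of three events. Death from any cause counts. A hospital admission or a health-centre consultation counts only if it was for infection.

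SAP 1.6.3 rules out imputing outcome data and then makes one open exception: "for a particular event, we will assume that it was not caused by an infection if no information is obtained".

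Information on cause comes from two routes. For admissions it is the participant's (sometimes a relative's) telephone account; SAP 1.5.2(d) describes the outcome as "Self-reported admission with symptoms or diagnosis classified as caused by infection". For recorded consultations it is the health-centre books (SAP 1.4.2). The Protocol (Methods, follow-up on consultations) adds that a project assistant notes the main cause when issuing the voucher.

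Under the Protocol's description of the intervention, controls receive advice but neither OPV nor a placebo. Neither document says who classifies an event as infectious, or whether that person is kept from the allocation.

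The sensitivity analyses of outcome definition in SAP 2.6.1 are listed as "Narrower definitions of the planned outcomes". SAP 1.6.2 also gives the secondary outcomes a robustness role.

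**The concern.** At the planning figures, most of the primary composite depends on an attributed cause. If a cause is recorded less often in one arm, the rule removes more events from that arm and the hazard ratio moves without any effect of OPV. It can move either way, so the rule could produce an apparent benefit, produce an apparent harm or hide a real benefit. Because participants know their arm, equal completeness of telephone reporting cannot be taken as given. A reader of the final report would also be unable to judge the matter, since the number of events affected in each arm is not among the planned outputs. The missing-information proportions in SAP 2.1 concern background factors.

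**Working it through.** **Inputs from the documents**

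- Size: "With a samples size of 3400, half getting OPV", so 1700 per arm.
- Error rates: "reduction) with 80% power and alpha of 0.05" (Protocol, sample size); "All statistical tests will be 2-tailed" (SAP 1.6.1).
- Planned six-month risks: 10% control, 7.2% OPV (Protocol, sample size).
- Mortality: "which has been around 2% in this age group in our study area". The text does not settle whether this is per six months or per year. I use d = 2%, with 1% as the alternative.
- Non-fatal infection events: q = 10% − 2% = 8% (9% if deaths are 1%).

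**Input that is assumed.** The share m of non-fatal infection events with no cause information. The documents give no figure, so a range is shown.

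**Step 1: the plan's own figure.** With p1 = 0.10, p2 = 0.072 and mean p̄ = 0.086:

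n per arm = [1.96·√(2p̄(1−p̄)) + 0.8416·√(p1(1−p1) + p2(1−p2))]² / (p1−p2)² = (0.777 + 0.333)² / 0.028² ≈ 1573.

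At 1700 per arm, power is 0.83. With a continuity correction, 1644 per arm are needed and power at 1700 is 0.814. The stated 80% is reproduced.

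**Step 2: the rule under no true effect.** Deaths are always counted and unknown-cause events are dropped, so the observed risk in an arm is p = d + q(1 − m). The risk ratio is p(OPV)/p(control), and HR = ln(1 − p(OPV)) / ln(1 − p(control)). The last column is the chance of a two-sided p ≤ 0.05 from an unpooled two-proportion z-test.

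| Unknown cause, control / OPV | Risk, control | Risk, OPV | Risk ratio | HR | Chance of p ≤ 0.05 |
|---|---|---|---|---|---|
| 10% / 10% | 0.092 | 0.092 | 1.00 | 1.00 | 5% |
| 10% / 15% | 0.092 | 0.088 | 0.957 | 0.954 | 6.9% |
| 10% / 20% | 0.092 | 0.084 | 0.913 | 0.909 | 13.1% |
| 10% / 30% | 0.092 | 0.076 | 0.826 | 0.819 | 39.1% |
| 20% / 10% | 0.084 | 0.092 | 1.095 | 1.100 | 13.1% |

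Example, 10% / 20%: control 0.02 + 0.08 × 0.90 = 0.092; OPV 0.02 + 0.08 × 0.80 = 0.084; ratio 0.084/0.092 = 0.913. With deaths at 1%, the 10/15 and 10/20 rows become 0.951 and 0.901.

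**Step 3: how large a gap would imitate the planned effect.** Setting the ratio to 0.72 and d = 2%, control at 0% unknown needs OPV at 35%, since (0.02 + 0.08 × 0.65)/0.10 = 0.72. With d = 1% it needs 31%. With control at 10%, OPV must be at 42% or 38% respectively.

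**Step 4: equal shares.** The ratio is unchanged if the effect is the same on deaths and on non-fatal events, but events are lost. With a true 28% reduction, power without continuity correction falls from 0.83 to 0.795 at 10% unknown and 0.755 at 20%.

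**Step 5: which planned analyses touch the rule**

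- Narrower definitions (SAP 2.6.1): none adds unknown-cause events back.
- TMLE (SAP 2.6.2): addresses baseline imbalance, with the same outcomes.
- Secondary (c), mortality: not exposed to the rule, so it cannot test it.
- Secondary (d) and (e): cause-dependent, so they carry the same rule.
- Secondary (a): built on listed symptoms, so largely free of the rule, but it measures milder illness.
- Secondary (f): any facility, but still restricted to infectious disease.

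**Step 6: recoding.** Counting unknown-cause events as infection gives 0.02 + 0.08 = 0.10 in both arms, a ratio of 1.00, in every row of the table. This holds because all unknown-cause events in this model are true infections. In practice some will not be, so the recoded analysis is the opposite extreme of a rule common to both arms and does not correct the bias.

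**The case against.** The strongest reply is that the rule may reach few events. It applies only where no information was obtained. Each telephone call goes through a symptom list and asks the reason and diagnosis for any contact with care (SAP 1.4.1). The books supply symptoms, tests and treatment, and the voucher procedure supplies a main cause. This stands, and a table by arm would confirm or refute it.

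A second reply is that the secondary outcomes already offer a check. An artefact of cause reporting would tend to show in (d) or (e) without a matching pattern in (a) and (c). This stands in part. A reader might infer that no planned analysis could reveal a problem, and that goes too far. But the contrast would raise suspicion only, since milder illness and death may respond differently from admissions for other reasons.

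A third reply is that no difference in cause reporting is documented. This is correct. SAP 1.6.1 reports more refusal in the intervention arm, but refusal happens at enrolment, before any outcome is collected. The same health centres serve both arms, and nothing says that their staff know the allocation. The unmasked design therefore bears mainly on telephone reports and on the later classification step.

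The scenarios are also simple. One share covers all non-fatal events, and a participant with an unknown-cause event is assumed to have no later qualifying event, which tends to overstate the shift.

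Finally, a reader might say that the SAP contradicts itself by declining to impute and then imputing. It does not: the exception is openly stated. What is missing is a test of it.

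**Conclusion.** The point holds as an untested assumption in the primary analysis. The documents do not support a claim that the primary hazard ratio is biased, because they report neither how often cause is unknown nor any imbalance in it.

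If the shares differ by 5 to 10 points, the ratio under no effect moves to about 0.96 to 0.91, or to about 1.10 if the 10-point gap is reversed. On the log scale the 10-point case is about 28% of the planned effect (ln 0.913 / ln 0.72 = 0.28). A reader might infer that the rule alone could imitate the whole planned reduction, but Step 3 shows that this needs a gap of roughly 30 points, which nothing in the documents suggests.

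These sizes rest on the 2%/8% split and on assumed shares. The change is worth making because it is cheap and bears directly on how the primary result is read.

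**What to change.** 1. **SAP 1.6.3:** report, by arm, the number of admissions and recorded consultations for which no cause information was obtained.
2. **SAP 2.6.1:** add one sensitivity analysis that repeats the primary model with those events counted as infections. A version using admission or recorded consultation for any reason, together with death, is an optional supplement. It adds events that OPV is not expected to prevent, so its hazard ratio should lie closer to 1, and it remains open to differences in care-seeking between arms.
3. **SAP 1.5, as a separate point:** state that symptom and diagnosis text is classified as infection or not from a file without house number or group, before allocation is merged. This protects the coding of known causes and does nothing for missing ones, so it does not replace items 1 and 2.

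The cost is one extra model, one table and a file-handling step, using information that the plan already collects. If the table shows few unknown causes in both arms, the matter is closed.

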1.6.4 Test for proportional hazards

To test the proportional hazards assumption, a required assumption of the Cox regression, we will perform formal significance tests based on Schoenfeld residuals. In addition, we will assess proportionality by allowing the hazard ratio to interact with the underlying timescale to identify a possible time trend. Finally, we will assess proportionality graphically via log-log survival curves.

Significance tests based on Schoenfeld residuals will be performed via the Stata command *estat phtest, detail* leading to both a global test and a test for each covariate, the latter being relevant only when we study effect modifications. Presentation of log-log survival curves will be undertaken via *stphplot*. Finally, possible interactions between hazard ratios and the underlying time scale will be further investigated via the *stcox* procedure and the *tvc()* option. For the models including effect modifications we will construct a new interaction variable (i.e., a four-level variable representing the interaction) such that a graphical assessment of proportionality can be undertaken assessing the four-level variable in a log-log survival plot.

If we identify evidence for non-proportionality, we will still report the marginal hazard ratios but supplement this measure by hazard ratios for 2-3 properly selected categorical time-periods identified based on the aforementioned proportionality investigations.

2. Analyses

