2.3 Analyses of secondary outcomes

For our secondary outcomes a) episodes with self-reported infectious disease morbidity reported through the monthly follow-up calls, b) episodes with self-reported infectious disease morbidity suspected to be caused by COVID-19 (three or more of the following: fever, cough, sore throat, extreme fatigue, loss of smell and/or taste) and f) reported consultation for infectious disease, we will analyse repeated events data sets including all individuals for whom information was obtained through the telephone follow-up.

For the separated components of the composite outcome the population depends on the outcome assessed: c) mortality is for all individuals, d) hospital admissions for all individuals for whom a telephone follow-up was conducted and e) recorded consultation for all individuals alive in the study area.

The analyses of the secondary outcomes are described in more detail in table 2, 3 and 4.

¹If we identify evidence for non-proportionality, we will still report the marginal hazard ratios, but supplement this estimate by hazard ratios for 2-3 properly selected categorical time-periods identified based on the aforementioned proportionality investigations.

² If there is indication of non-proportionality based on assessment of the log-log curves, we will test for non-proportionality by replacing the term `tezp(_t)` with `tezp(_t>s)` for specific values of `s`.

Table 2: Analyses of secondary outcomes (a, b, d, f) – reported morbidity outcomes

Population	Per-protocol population
Observation period	From: enrolment To: 183 days after enrolment Censoring: Death, Date of loss to follow-up (last telephone interview)
Failure definition	
 a) Self-reported infectious disease morbidity. b) Self-reported infectious disease morbidity suspected to be caused by COVID-19 d) Hospital admission for infectious disease f) Reported consultation for infectious disease 
Repeated events. Episodes within 2 weeks of each other will be considered as related to the same infection. Thus, a trial participant will re-enter the population-at-risk 14 days after the episode start, provided that there has been a period without reported symptoms in the meantime.

Statistical tools	Repeated Cox-proportional hazards model, adjusted for the zone (stratification variable in the randomisation), age and box1 factors. Robust standard error to adjust for same-house clustering.

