2.4.2. Effect-modifier analyses of primary outcome. Changing effects during follow up

In the main analyses, observation time will be censored at 183 days after enrolment. However, the effect of OPV may vary over the 6 months and by season.

Furthermore, the risk of COVID-19 may also vary during the 6 months of follow-up: During 2020 and 2021, Guinea-Bissau experienced three waves of COVID-19 infections, during which the risk of COVID-19 has been elevated (figure). Based on this, we have identified periods of higher transmission: Before 1 October 2020, 1 January - 1 April 2021 and after 1 July 2021.

Finally, health staff have been on strikes during a large part of 2021. We will assess whether effects differ by periods of observation.

[figure not shown]

Figure: Number of confirmed COVID-19 cases per week in the Bissau sector (source www.ACCOVID.com).

Time varying effects will be investigated in the models described below.

Table 6. Potential effect modifiers of the primary outcome – changing effects during observation period

Population	Per-protocol population
Observation period	From: enrolment To: 183 days after enrolment Censoring: None
Potential effect modifiers	a) First 3 vs subsequent 3 months of follow up b) Season of follow-up (Rainy: June-November, Dry: December-May) c) Periods of intense transmission (Figure) d) Periods with health staff on strike
Failure definition	Death or first post-enrolment admission for infection or consultation for infection.
Statistical tools	Cox-proportional hazards model with interaction term, adjusted for the zone (stratification variable in the randomisation), age and box1 factors. Robust standard error to adjust for same-house clustering.
Outline stata code For analysis:	<pre>stset outcome, f(combinedoutcome=1) origin(dateenrol) enter(dateenrol) exit(dateenrol+183) id(studyidnumber)</pre> 
a) Time since enrolment:
 <pre>g splitdate1=dateenrol+91 if dateenrol+_t >splitdate1 stsplitt time, at(0) after(splitdate1) replace time=time+1 recode time . =0</pre> <pre>stcox group#time time b11.zone b50.agegroup b1.box1var1 b1.box1var2 ..., vce(cl house)</pre> 
Where EfM is the potential effect modifier (categorical variable) and [box1var1] [box1var2] etc. are the background factors from Box1 which affect the [group]-estimate for the main outcome by more than 10%
 
b) Splitting the observation time 1 December 2020 and 1 June 2021 to define rainy season (before 1 December and after 1 June) and dry season

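### The Schoenfeld check for the primary model points to a global test made up mostly of zone terms, and the follow-up step test uses a cut-point chosen from the plot; neither is a sound basis for saying when OPV works.

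*SAP*

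**What the plan says.** SAP 1.6.4 plans three checks of proportionality: Schoenfeld residual tests, an interaction of the hazard ratio with follow-up time, and log-log survival curves. The Schoenfeld step uses `estat phtest, detail`, described as "leading to both a global test and a test for each covariate, the latter being relevant only when we study effect modifications".

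The Table 1 code runs that command after a model with group, zone indicators, age bands and any retained Box 1 factors. It also fits a second model with `tvc(group)` on continuous time, with zone and age moved into the strata.

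Footnote 2 adds a step: "If there is indication of non-proportionality based on assessment of the log-log curves, we will test for non-proportionality by replacing the term" for continuous time with an indicator for time beyond chosen values of s. If evidence of non-proportionality is found, the overall hazard ratio is still reported and is supplemented by "hazard ratios for 2-3 properly selected categorical time-periods identified based on the aforementioned proportionality investigations".

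Separately, Table 6 fixes an effect-modifier analysis in advance, "a) First 3 vs subsequent 3 months of follow up", split 91 days after enrolment. The SAP does not say which of the three checks counts as evidence if they disagree.

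**The concern.** For the primary result, the assumption that matters is that the OPV hazard ratio is constant over follow-up. The Schoenfeld row for group tests exactly that, with one degree of freedom. By calling the covariate rows relevant only to effect modification, the SAP leaves the global test as the Schoenfeld result for the primary model. That test pools group with every zone and age term. A change in the OPV effect is diluted, and a zone effect that drifts over time can cause rejection when OPV is perfectly proportional.

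The second weakness is circularity. A cut-point picked because the curves seem to part there, and then tested on the same data, does not give a 5% test. Periods chosen that way will tend to show contrasting hazard ratios by chance. SAP 1.6.2 makes no correction for multiple testing.

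At stake is the credibility of any statement that OPV worked early, or stopped working late.

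**Working it through.** **Inputs.**
- Sample size: "With a samples size of 3400, half getting OPV", so 1700 per arm (Protocol, Sample size).
- Risks: "severe morbidity after 6 months of follow-up from a total of 10% to 7.2"%, so 1700 × (0.10 + 0.072) = 292 planned events.
- Error rates: "with 80% power and alpha of 0.05"; "All statistical tests will be 2-tailed" (SAP 1.6.1).
- Zones (SAP 1.2): 9 + 8 + 9 + 3 + 5 = 34.
- Age: 5-year bands, number not stated. Assumed 7 to 9.

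**1. The plan's own figure.** Schoenfeld events = 4 × (1.960 + 0.842)² / (ln 0.72)² = 291; 291 / 0.086 = 3384 participants, against 3400 planned. Power with 292 events is 80.2%. The planning figure is reproduced, so 292 events is a fair basis. The documents give no power or error rate for the proportionality check itself.

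**2. Degrees of freedom.** 1 (group) + 33 (zones) + (age bands − 1) = 40, 41 or 42 for 7, 8 or 9 bands, before any Box 1 term. Zones make up 79% to 83%.

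**3. Dilution.** A signal with 80% power on 1 df has noncentrality (1.960 + 0.842)² = 7.85. Referred to 41 df (critical value 56.94), the same signal has 21% power.

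**4. Waning scenarios (assumed).** Take about 85 control events in each half of follow-up and OPV hazard ratios h₁ then h₂. The noncentrality for a step at mid follow-up is

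λ = (ln h₂/h₁)² / [1/(85h₁) + 1/85 + 1/(85h₂) + 1/85].

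A test linear in time captures 0.75λ, because the squared correlation of a mid-point step with uniform time is 3/4. For 0.5 then 1.0: λ = 0.693² / 0.0588 = 8.17 and 0.75λ = 6.13.

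| HR, first then second half | Global, 41 df | Group × linear time, 1 df | Fixed 3-month split, 1 df |
|---|---|---|---|
| 0.4 then 1.0 | 27% | 88% | 95% |
| 0.5 then 1.0 | 17% | 70% | 82% |
| 0.6 then 1.0 | 11% | 47% | 59% |
| 0.6 then 0.85 | 7% | 24% | 31% |

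Using 40 or 42 df moves the global column by less than half a percentage point. In 400 simulated trials per scenario (34 zones, 8 age bands, house clustering ignored), 0.5 then 1.0 gave 16% for the global test and 72% for the group row.

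**5. Rejection because of zones.** With every term proportional, the simulated global test keeps its size (4.8%). With OPV proportional but zone log-hazards (SD 0.6) reversing sign at mid follow-up, the global test rejected in 100% of trials and the group row in 5.5%. That scenario is deliberately strong. An approximation with smaller reversals gives about 8%, 24% and 59% for SD 0.1, 0.2 and 0.3.

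**6. Data-chosen cut-points.** Under exact proportionality, the step statistic at event fraction t behaves as B(t)/√[t(1−t)], with B a Brownian bridge. Over 20,000 null paths of 292 events, the chance that the most extreme cut passes 1.96 is:
- one fixed cut at day 91: 5%
- best of three cuts (quarter, half, three quarters of follow-up): 12%
- best of five monthly cuts: about 18%
- free search over days 20 to 160: about 40%

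**The case against.** The strongest reply is that the plan does not rest on the global test. The `tvc(group)` model is unconditional, has one degree of freedom, and keeps zones in the strata. Table 6 fixes the 3-month split whatever the check shows. `estat phtest, detail` prints the group row anyway, and no sentence in the SAP makes the global test decisive. All of this stands.

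It rules out several readings that a reader might infer:
- **That the plan misses waning of OPV.** The table above shows that the planned group tests detect strong waning. Their low power for moderate waning comes from about 292 events, not from the degrees of freedom.
- **That the check decides whether any period-specific effect is reported.** Table 6 already provides one, and the overall hazard ratio is reported in every case.
- **That the global test will raise a false alarm.** The documents give no zone-specific hazards and no enrolment order by zone. The 100% figure depends on the assumed reversal, and rejecting when zone effects truly drift is correct for the model as a whole. It only says nothing about OPV.
- **That the inflation is 40%.** Footnote 2 prescribes no maximal search and applies only if the curves suggest a departure. The true inflation is unknown.

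What the reply does not meet is the missing decision rule. If any one check suffices, a zone-driven global rejection or a plot-chosen s triggers extra OPV hazard ratios even when `tvc(group)` is clean. Those would then stand beside the pre-specified split as a competing account of timing.

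**Conclusion.** The point holds in a limited form. The Schoenfeld result that SAP 1.6.4 leaves in use for the primary model is poorly aimed at OPV: about 17% power where a one-degree-of-freedom group test has about 70%. It can also be driven by zones if their effects are non-proportional. A significance test at a cut read from the curves is not a 5% test; plausible rates run from about 12% to a worst case near 40%. The primary hazard ratio and its test are untouched, and the damage is confined to supplementary claims about when OPV works.

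This rests on the planned 292 events rather than an observed count, 7 to 9 age bands, no Box 1 terms, roughly even event times, the waning scenarios shown, and no allowance for house clustering.

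**What to change.** In SAP 1.6.4, Table 1 and footnote 2:

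1. Name the group row of `estat phtest` and the `tvc(group)` test as the deciding checks for the OPV effect, and do not use the global test for that decision.
2. Use the split already in Table 6, days 0–91 against 92–183, for both the step test and the period-specific hazard ratios.
3. Label any s or period chosen from the curves as exploratory, with no significance claim.

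Leave the main model as it is. Moving zone into the strata there is not needed to solve a problem with a diagnostic.

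The cost is wording only: no new data, and only output and a split that the SAP already specifies. The downside is that a time pattern that does not break near day 91 will be described only by the continuous-time interaction or by exploratory results.
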